A proposed randomized clinical trial of the effectiveness of a new breastfeeding- supportive texting program designed specifically for African-American/Black expectant women, as compared to a national maternal health texting program, on rates of exclusive breastfeeding at 2months; Short title: TOPS – Texting to Promote Breastfeeding).

XXXXXXXXXXXXXX

NCT06375655

01/19/2024

Objectives

Specific Aims

- 1. Demonstrate the feasibility and acceptability of a scaled-up program to deliver Team2BF text messages to AA/B expectant women considering breastfeeding.
- 2. Compare breastfeeding outcomes in the group receiving Team2BF with rates among those receiving Bright By Text.
- 3. Compare breastfeeding related knowledge and self-efficacy and social support as moderators of the relationship between the texting intervention and breastfeeding outcomes. (Exploratory aim)
- 4. Compare other key health outcomes (appointment attendance and vaccine receipt and book reading to infant) between the groups to verify that a focus on breastfeeding enhances rather than detracts from general maternal-infant health outcomes. (Exploratory aim)

Study Hypotheses

- Participants will find the Team2BF intervention acceptable as measured by >90%
 continuation, by >75% top score helpfulness of messages for breastfeeding and >75%
 endorsement of friend and family referral.
- 2. Participants receiving Team2BF will have significantly higher exclusive breastfeeding rates at 2 months as compared to participants receiving Bright By Text.
- 3. Breastfeeding knowledge, perceived social support for exclusive breastfeeding and self-efficacy will positively moderate the relationship between texting and breastfeeding outcomes, with those in the Team2BF group demonstrating a significantly greater increase in these domains with time as compared to the Bright By Text group.
- 4. Participants in both groups will have >75% rates of attendance among mothers at the (2-6 weeks) postpartum obstetrical visit and >75% rates of attendance and vaccine receipt for infants at the 2 month (6-12 weeks) well care visit.

Background

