In this research, we follow up on prior work that assessed the feasibility and acceptability and content of a culturally-tuned Breastfeeding-supportive Text Messaging Library intended for AA/B women. That work (TEAM2BF, STUDY20221270) demonstrated that expectant and delivered AA/B women found the text messaging process and content acceptable and helpful. None stopped any or all of the messaging, and approximately 6 messages were revised as recommended by participants. In this current study we aim to obtain preliminary efficacy data by comparing this texting library aimed at promoting breastfeeding to a professionally endorsed national maternal child health texting program, Bright By Text, whose focus is not breastfeeding. By comparing the TEAM2BF texting program to Bright By Text, we can compare whether message content impacts breastfeeding initiation and exclusivity at 2 months. The study design is equitable for participants in that both programs use a similar approach (texting), both are designed to be accessible to minoritized women of low socioeconomic status, and the comparator (Bright By Text) has demonstrated benefits.[16] This study aims to address identified gaps in breastfeeding support for AA/B women that we hope can ultimately reduce racial inequities in breastfeeding rates.

Inclusion and Exclusion Criteria

| | | Inclusion Criteria - mothers |
|--|--|---|
| 1. Expectant women initiating obstetrical care <34 weeks or at any | | Expectant women initiating obstetrical care <34 weeks or at any prenatal visit up |
| | | to 34 weeks gestation |

| 2. | Daily access to a mobile phone with text message capabilities, |
|----|--|
| 3. | 18 years or older (i.e., adult), |
| 4. | Self-identify as African-American/Black, |
| 5. | English speaking, and |
| 6. | Infant feeding plan of "might or will breastfeed". |
| 7. | Receive care at Ahuja Midtown or MAC1200 |

| | Exclusion Criteria |
|--|--------------------------------------|
| 1. | Minors |
| 2. Committed to feeding formula only to their infant | |
| 3. | No mobile phone with text capability |

| | Inclusion Criteria - infants |
|----|--------------------------------|
| 1. | Infant of maternal participant |

| | Exclusion Criteria -infants | |
|----|---------------------------------------|--|
| 1. | 1. Not infant of maternal participant | |

Number of Research Participants

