We will enroll up to 80 participants. Infants are a secondary population and we will enroll up to 85 infants (85 not 80 to allow for inclusion of multiples if this occurs).

Recruitment Methods

Maternal participants will be recruited via OB provider schedules at Ahuja Rainbow Center for Women and Children (ARCWC- Midtown location) and MacDonald 1200. Women will be approached in person before or after clinic visits with the permission of the OB provider. The study may be introduced in a group setting (CenteringPregnancy) but all consent procedures will be individual and private.

Setting

Expectant women will be recruited at UHCMC locations ARCWC and Mac1200. The intervention itself is virtual so following the consent process and enrollment there will not be inperson contact (except for the optional interview which can be by telephone or in person as preferred).

Consent Process

Potential participants will be recruited as above and approached in person before or after clinic visits with the permission of the OB provider. Signed consent will be obtained in person following an informed consent procedure with time for questions. The potential participant's exam room is a private place and if this is not available, we will find an unused office or conference space to have a private consent process. Potential participants who are interested will discuss the research with a study team member using the informed consent document. Family or friends may join the discussion if the potential participant chooses, and all questions will be answered. The potential participant can decide to participate and sign the informed consent or can decide to not join or can think about it further and call the study team if she decides to join.

Sharing of Results with Research Participants

☑ Results will not be shared with research participants.

Results are very preliminary and the number of participants is small so to avoid identifiability we will not provide results.

☑ Results will not be shared with research participants' doctors

Study Design

A prospective block-randomized two arm unblinded cohort study.

Study Procedures

1- Intervention – study procedures. In summary these include receiving texts, completing surveys and interviews, and permitting review of the medical record.

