| | Breastfeeding Knowledge Quiz (4 | | | | |
| | questions – answers follow) | | | | |
| | Breastfeeding Self-Efficacy Scale (14 | | | | |
| | items) | | | | |
| One week after | Infant Feeding Information-what milk is | 2 minutes | | | |
| delivery (PP) | baby drinking? | | | | |
| One month PP | Infant Feeding Information | 2 minutes | | | |
| Two months PP | Infant Feeding Information | 15 minutes | | | |
| | Breastfeeding Knowledge Quiz | | | | |
| | Breastfeeding Self-Efficacy Scale | | | | |
| | Breastfeeding Social Support Scale (16 | | | | |
| | items) | | | | |
| | Maternal Satisfaction (6 questions) | | | | |
| Three months PP | Infant Feeding Information | 3-4 minutes | | | |
| | Healthy Development (1 question) | | | | |
| | Maternal Satisfaction (6 questions) | | | | |
| Six months PP | Infant Feeding Information | 8-17 minutes | | | |
| | Healthy Development | | | | |
| | Maternal Satisfaction (6 questions) | | | | |
| | Study Thank you Survey | | | | |

Data to be Collected for your study

Outcome Measures

Aim #1 - Acceptability

Receipt of messages measures acceptability because participants can easily end messaging; if at least 90% of Team2BF participants continue receipt this will indicate acceptability of the intervention. This outcome will be enhanced by asking (a) a single 4 point Likert-scaled question

about the helpfulness of the texts for breastfeeding and (b) whether the participant would or would not refer a friend or family member to Team2BF.

Aim #2 – Breastfeeding Outcomes

The main outcome will be exclusive breastfeeding at 2 months because this is a meaningful milestone toward the public health goal of 6 months exclusive breastfeeding. We will assess partial and exclusive breastfeeding at hospital discharge and at 1, 2, 3 and 6 months post delivery using the World Health Organization definitions for exclusive and partial breastfeeding. We will also assess timing of discontinuation of breastfeeding if this occurs.

Aim #3 – Moderators of Breastfeeding Outcomes (Exploratory aim)

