By measuring breastfeeding knowledge at enrollment and again at 2 months we will assess for change in knowledge and for relationship to the main breastfeeding outcome. By measuring self-efficacy at enrollment and 2 months we will assess for changes in self-efficacy and relationship to the main breastfeeding outcome. We will assess perceived social support for exclusive breastfeeding at 2 months to compare those who did and did not achieve this goal.

Aim #4 – Non-breastfeeding Health Outcomes (Exploratory aim)

We will compare other key health outcomes between the groups that have been documented as relevant Bright By Text outcomes, as a direct Bright By Text outcome and a proxy to verify that a focus on breastfeeding enhances rather than detracts from general maternal-infant health outcomes. Attendance at the maternal postpartum check and attendance at the infant 2, 4 and 6 months well care appointments, including whether age-appropriate vaccines were received, will be assessed, as well as a measure of literacy (number of days per week reading books to baby).

Management of surveys – Generally participants will complete the enrollment timepoint surveys electronically, but if their phone is not able to photograph the QR codes that lead to the enrollment surveys, these will be administered on paper. The documents will be maintained on and transferred on the person of the study team member to the CCHP (Center for Child Health Policy) Office MCCO 650. The surveys will be kept in a locked cabinet with study team member access only, and after entry into REDCap will be retained until data analysis is complete.

Data Analysis Plan

Populations of each group will be compared using descriptive statistics (means and ranges, percents and frequencies). The main outcome of breastfeeding exclusively at 2 months will be compared between the two arms (texting groups) controlling for factors known to impact breastfeeding rates, as well as site of enrollment.

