To calculate sample size both current and near past breastfeeding rates are relevant. At the Rainbow Pediatric Practice (RPP, IRB # 11-16-07, using a 3 month annual snapshot) data from 2016-2020 inclusive years for full term and late preterm infants not admitted to Neonatal Intensive Care Unit who have an appointment in RPP in first month of life: 89/808 infants (11%) were exclusively breastfed at 2 months. Women Infants and Children Supplemental Feeding Program (WIC) Cuyahoga County data aligns with this estimate, showing "Fully Breastfed Infants" (defined as infants of participating breastfeeding women do not receive formula from the WIC Program) for the fiscal year 2021 with 594/5188 infants (11.4%) fully breasted. An increase from 11% to 14% would be clinically meaningful, and to achieve this with 80% power, alpha 0.05 (SD of not more than 5%) we need 36 mother-infant dyads per group, which is 72; and allowing for 10% attrition we aim to enroll 40 mothers per group (80 total).

Without published data on breastfeeding from Bright By Text participants, a 5% point difference between the two arms in this outcome can be considered clinically meaningful. The timing of breastfeeding cessation is the inverse of partial or exclusive breastfeeding and will be compared between the two arms at end of study (6 months); a 1 month difference between the groups can be considered clinically meaningful.

Risks to Research Participants

There is a risk of breach of confidentiality due to ongoing text messaging but this will be protected against by careful management of the texting system by study team members and by protecting and securing the data received. There is a risk of emotional distress if a participant's anxiety about breastfeeding is increased by receiving messages about breastfeeding from either texting program – this will be mitigated by providing resources through the messages, by the ability to unsubscribe promptly, and in the informed consent by emphasizing that this is a research study and breastfeeding help can be obtained from her health providers or the Ohio Breastfeeding Hotline. There is a risk of data overage or charge depending on what plan a participant is on – we cannot mitigate this, but all participants can unsubscribe whenever they choose. All participants can text STOP to unsubscribe at any point with either study arm and withdraw themselves from the research.

Provisions to Protect the Privacy Interests of Research Participants

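### The claimed 80% power for 11% versus 14% with 36 dyads per arm treats a yes/no outcome as a continuous one; actual power is about 7% two-sided or 10% one-sided.

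*Combined protocol and SAP*

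**What the plan says.** Under Outcome Measures, Aim #2, the protocol says: "The main outcome will be exclusive breastfeeding at 2 months". The Data Analysis Plan compares this between the arms, "controlling for factors known to impact breastfeeding rates, as well as site of enrollment". It names neither the test nor whether it is one- or two-sided. Study Hypothesis 2 is directional: "Participants receiving Team2BF will have significantly higher exclusive breastfeeding rates at 2 months".

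The sample-size paragraph takes 11% as the current rate, from 89 of 808 infants at the local practice, and calls a rise to 14% clinically meaningful. It continues: "to achieve this with 80% power, alpha 0.05 (SD of not more than 5%) we need 36 mother-infant dyads per group". Allowing 10% attrition, it arrives at 40 mothers per group and 80 in total. The next paragraph adds that "a 5% point difference between the two arms in this outcome can be considered clinically meaningful".

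Elsewhere the ambition is more modest. The Background says "In this current study we aim to obtain preliminary efficacy data", and the section on sharing results says "Results are very preliminary and the number of participants is small".

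**The concern.** A sample-size calculation for two proportions takes no separate SD, because each rate determines its own. An SD of 5 percentage points therefore suggests a formula for means applied to a yes/no outcome. Thirty-six per arm is also implausibly small for a 3-point difference at rates near 11%.

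The paragraph is the only statistical justification for the sample size. If the 80% is wrong, a non-significant result is the expected outcome even when Team2BF works as planned, yet a reader relying on the stated power would count it as evidence that it does not. A significant result would have to show a gap far above 3 points, so it would overstate a true 3-point effect.

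**Working it through.** **Inputs (Data Analysis Plan).** Rates 0.11 and 0.14; alpha 0.05; power 80%; SD 5 points; 36 per arm; 10% attrition. Sidedness is not given, so both versions are shown.

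**1. Reproducing 36.** For two means, n per arm = 2(z_α + z_β)² × SD² / d², with d = 3 and SD = 5.
- One-sided: 2 × (1.645 + 0.842)² × 25/9 = 34.3. The t-test version gives 35.04, rounded up to 36.
- Two-sided: 2 × (1.960 + 0.842)² × 25/9 = 43.6 (t-test version 44.6), which does not match.
- Two-sided with SD 4.5, also within the stated ceiling: 35.3, rounded up to 36.

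Then 36/0.9 = 40 per arm. The plan's figure is reproducible, but only as a comparison of means. The text does not show which route was taken.

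**2. The SD of the actual outcome.** For a yes/no variable, SD = √(p(1 − p)): √(0.11 × 0.89) = 0.313 and √(0.14 × 0.86) = 0.347. That is 31 to 35 points, six to seven times the value assumed.

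**3. Sample size for two proportions.** n per arm = [z_α√(2p̄(1 − p̄)) + z_β√(p₁(1 − p₁) + p₂(1 − p₂))]² / (p₂ − p₁)², with p̄ = 0.125.
- Two-sided: (1.960 × 0.4677 + 0.842 × 0.4672)² / 0.0009 = 1,906.5, so 1,907.
- One-sided: (1.645 × 0.4677 + 0.842 × 0.4672)² / 0.0009 = 1,501.7, so 1,502.

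These are 53 and 42 times the stated 36. For the 5-point difference (11% versus 16%) the same formula gives 733 and 577.

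**4. Power of the planned sample.** Power was computed exactly, by summing binomial probabilities over all tables that the uncorrected chi-square test rejects.

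| Scenario | Two-sided | One-sided |
|---|---|---|
| 11% vs 14%, 36 per arm | 7.3% | 10.4% |
| 11% vs 14%, 40 per arm (no attrition) | 7.5% | 10.7% |
| 11% vs 16%, 36 per arm | 10.0% | 14.9% |

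Of the 7.3%, about 1.1 points are rejections in the wrong direction, so power to show Team2BF better is 6.2%. Fisher's exact test gives 2.8% two-sided and 4.9% one-sided for 11% versus 14%. With 36 per arm and 11% in control, 80% power requires about 39% in Team2BF (two-sided) or 35% (one-sided).

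**5. What the data would look like.** Expected events are 36 × 0.11 = 4.0 and 36 × 0.14 = 5.0. With 4 of 36 in control, two-sided significance needs 11 of 36 in Team2BF: z = (7/36)/√(0.2083 × 0.7917 × 2/36) = 2.03. That is 31%, a 19-point gap. One-sided, 10 of 36 suffices (z = 1.79). When the true rates are 11% and 14%, Team2BF's count is equal to or below control's 41.8% of the time (13.3% ties, 28.5% strictly lower).

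The unadjusted Wald 95% half-width is 1.96 × √((0.0979 + 0.1204)/36) = 0.153. For 4/36 versus 5/36 the Newcombe interval runs from −13 to +19 points.

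**6. Sensitivity to the control rate (assumed values).** At control rates of 5%, 20%, 30% and 40%, a 3-point gain with 36 per arm has 6% to 8% power two-sided and 9% to 14% one-sided. At control rates of 20% and 30%, the rate detectable with 80% two-sided power is about 51% and 62%, and the half-width for a 3-point difference is about 19 and 21 points.

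**The case against.** The best defence is that this is a small preliminary study and says so twice; nothing in the documents triggers action on a null result. That justifies enrolling 80 mothers. It does not withdraw the explicit power statement, or a hypothesis that predicts a significant difference.

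The planned covariate and site adjustment could add precision. As a rough linear-model guide, closing the gap would need covariates explaining 1 − 36/1,907 = 98% of outcome variance (1 − 36/1,502 = 98% one-sided). The guide does not carry over exactly to a logistic model, but no plausible adjustment comes near that.

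Two points stand and shape the fix:
- The 11% comes from infants not selected on feeding plan, whereas the trial enrols women who are at least considering breastfeeding. The documents give no control rate for them. The detectable rate and the interval width move with that rate; the low power for a 3-point gain does not.
- With about nine events expected in total, an adjusted risk difference could be unstable. The ±15 points is an unadjusted figure.

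It is also fair to say that the sums themselves are consistent from 36 to 80. The fault is the outcome model they rest on.

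**Conclusion.** The concern holds. The 80% power claim and the SD of 5 points cannot be defended for a yes/no outcome. With 36 evaluable dyads per arm and true rates of 11% and 14%, power is 7.3% two-sided or 10.4% one-sided (uncorrected chi-square, exact, unadjusted), so non-significance is expected in about 93% or 90% of such trials. Full retention, a one-sided test, the 5-point difference at 11% control, and a 3-point gain at the other control rates examined all leave power at or below about 15%. This must be corrected before the sample-size paragraph is relied on.

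**What to change.** Keep 80 mothers, the main outcome and the planned adjustment. In the Data Analysis Plan:

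- Delete the SD allowance and the 80% power claim.
- State whether the test is one- or two-sided.
- State that, if the control rate is 11%, 36 evaluable dyads per arm give about 7% (two-sided) or 10% (one-sided) power for a rise to 14%, 80% two-sided power only near 39%, and an unadjusted 95% CI of roughly ±15 points. Add the figures for one or two higher control rates, marked as assumptions.
- Say which of the 3-point and 5-point differences is the planning difference between arms.
- Report the adjusted between-arm risk difference with its 95% CI as preliminary efficacy data. Name a short covariate list, and give the unadjusted difference alongside because events will be few.
- State that a non-significant result will not be read as absence of effect.

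The cost is text in the sample-size and analysis paragraphs plus one reporting choice. No participants, visits or data are added. The stated power becomes far less favourable, and the sample size will then rest on the study's preliminary purpose.

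### Two differences (3 and 5 percentage points) are called clinically meaningful for the main outcome without a stated role for each, and the claimed 80% power at 36 per group holds for neither

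*Combined protocol and SAP*

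**What the plan says.** The protocol's Outcome Measures section (Aim #2) fixes the endpoint: "The main outcome will be exclusive breastfeeding at 2 months". This is a yes/no outcome for each dyad.

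The Data Analysis Plan takes its reference rate from clinic data, "89/808 infants (11%) were exclusively breastfed at 2 months", and then states: "An increase from 11% to 14% would be clinically meaningful". With "80% power, alpha 0.05 (SD of not more than 5"%), it concludes "we need 36 mother-infant dyads per group, which is 72" and, "allowing for 10% attrition we aim to enroll 40 mothers per group (80 total").

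The next paragraph notes that no breastfeeding data have been published for Bright By Text participants and says that "a 5% point difference between the two arms in this outcome can be considered clinically meaningful". The natural reading of the outcome meant there is exclusive breastfeeding at 2 months. The text does not say how this figure relates to the 3-point one.

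Study Hypothesis 2 is directional and refers only to significance: "Participants receiving Team2BF will have significantly higher exclusive breastfeeding rates at 2 months". The Data Analysis Plan promises a comparison adjusted for factors known to affect breastfeeding and for enrolment site. It names no test or model, does not state one- or two-sided testing, and does not mention a confidence interval.

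**The concern.** Adjacent paragraphs give two sizes of effect the same label for what reads as the same outcome. The 3-point figure feeds a two-group calculation, so it already acts as a between-arm difference. The 5-point figure has its own rationale and is followed by a similar benchmark for time to cessation (1 month). With no analysis method or interval specified, these sentences are the plan's only guide to judging the size of the result.

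Two things are at stake. A reader told that the trial has 80% power will take a null result as informative and a 3- or 5-point observed difference as a finding. And the power statement cannot be corrected until the plan says which difference it refers to, because the required sample size differs about 2.6-fold between the two.

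**Working it through.** **Inputs.** Control rate 11% (89/808 = 11.0%); 14% from the sample-size sentence; 16% = 11% + 5 points; power 80%; alpha 0.05; SD 5%; 36 evaluable and 40 enrolled per group. All are from the Data Analysis Plan. Sidedness is not stated, so both are shown where it matters.

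**1. Reproducing the 36.** For two means, n = 2(z_alpha + z_beta)² × SD²/delta² per arm, with delta = 3 and SD = 5.
- One-sided: 2 × (1.645 + 0.842)² × 25/9 = 34.3, so 35. The t-test version gives 35.04, so **36**, which matches.
- Two-sided: 43.6, so 44; the t-test version gives 45. Neither matches.
- Attrition: 36/0.90 = 40, which matches.

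The 36 therefore comes from the 3-point difference, treated as a one-sided comparison of means. The 5-point figure does not enter; in the same formula it would give 13 to 17 per arm.

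**2. Why that formula does not apply.** The SD of a yes/no outcome is √(p(1−p)): √(0.11 × 0.89) = 0.313 and √(0.14 × 0.86) = 0.347. That is 31 to 35 points, not 5.

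**3. Sample size as two proportions.** With p̄ the mean of p1 and p2,

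n = [z_alpha √(2p̄(1−p̄)) + z_beta √(p1(1−p1) + p2(1−p2))]² / (p2−p1)²

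Two-sided 0.05, 80% power:
- 11% vs 14%: (1.960 × 0.4677 + 0.842 × 0.4672)²/0.0009 = 1,906.5, so **1,907 per arm** (one-sided 1,502).
- 11% vs 16%: (1.960 × 0.4833 + 0.842 × 0.4820)²/0.0025 = 732.1, so **733 per arm** (one-sided 577).
- Ratio: 1,907/733 = 2.6.

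**4. Power at 36 per arm, in favour of Team2BF, two-sided 0.05.** Power = 1 − Φ[(1.96 × SE0 − difference)/SE1], where SE0 is the pooled and SE1 the unpooled standard error.
- 11% vs 14%: (1.96 × 0.07795 − 0.03)/0.07787 = 1.577, so **5.7%**.
- 11% vs 16%: (1.96 × 0.08055 − 0.05)/0.08033 = 1.343, so **9.0%**.

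Counting rejections in the wrong direction as well gives 6.7% and 9.5%. One-sided 0.05 gives 10.4% and 15.2%. At 36 per arm, 80% power (two-sided) needs roughly 11% vs 39%.

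**5. Precision at 36 per arm.** The 95% CI half-width is 1.96 × √(0.11 × 0.89/36 + 0.14 × 0.86/36) = **15.3 points**; with 16% in place of 14% it is 15.7.

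**6. Chance of reaching either figure with no effect.** With both arms truly 11%, exact binomial calculation gives the probability of an observed difference favouring Team2BF of at least 3 points as **28.3%** (36 per arm) or **29.4%** (40 per arm). The probabilities for at least 5 points are identical.

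**7. Why they are identical.** In equal arms the crude difference moves in steps of one mother. At 36 per arm the steps are 2.8, then 5.6 points; at 40 they are 2.5, then 5.0. No crude difference falls from 3 to under 5 points. Some unequal completer counts open the gap: with both arms at 11%, the chance of landing in it is about 7% for 35 Bright By Text vs 37 Team2BF, and about 13% for 36 vs 35. A covariate-adjusted estimate is not confined to these steps.

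**The case against.** A reader might infer that the trial has no single target, or that its sample size contradicts its own interpretation rule. The documents support neither. The sample-size sentence has one identifiable input, 3 points, and 36 reproduces from it. Nowhere is 5 points called a minimum, a threshold or a success criterion, and Hypothesis 2 asks only for a significant difference. Since 5 exceeds 3, both can be clinically meaningful at once.

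A milder reading is also available: 11% to 14% is a rise over the historical clinic rate, while 5 points is a between-arm figure offered because comparator data are lacking. This does not fully resolve the matter, because the 3-point figure is used in a two-group calculation. It does mean that explaining each figure's role may serve as well as deleting one.

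A reader might also infer that investigators could claim or deny a meaningful result by choosing the sentence. For the crude difference with equal arms of 36 or 40 that cannot happen (step 7). It becomes possible only with some unequal completer counts or an adjusted estimate. Both are plausible here: the plan allows for attrition, mothers delivering before 36 weeks leave the study (Withdrawal of Research Participants), and adjustment is planned.

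Finally, the low power and wide interval come from the SD of 5%, not from having two figures, and choosing one figure would not cure them. That stands, and is why the power statement must be replaced as well. The Background describes the aim as preliminary efficacy data, which lowers the stakes but also favours estimation with an interval over a power claim.

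**Conclusion.** The point holds as a clarification plus a correction. Two differences are called clinically meaningful for what reads as the same main outcome, with no stated role for each. The 80% power attached to 36 per group is wrong for both: about 6% for 3 points and 9% for 5 points, with a confidence interval of about ±15 points. An observed advantage of either size is weak evidence, since it arises in more than one trial in four when there is no effect.

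These figures assume a simple two-sided 0.05 comparison of independent proportions, a control rate of 11% and 36 evaluable dyads per arm. One-sided testing or 40 per arm does not change the conclusion. The finding does not extend to a contradicted decision rule, because none exists, nor to a trial without a target.

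**What to change.** In the Data Analysis Plan:

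1. Name one between-arm difference in exclusive breastfeeding at 2 months as the target. The 3-point figure is the one the present calculation uses. Delete the other or state what it is for.
2. Remove the 80% power statement and the SD of 5%. Give instead the actual power for the chosen difference at 36 per arm by a two-proportion method, with sidedness stated, or the expected 95% CI half-width of about 15 points.
3. State that the between-arm difference will be reported with its 95% CI, and that an observed difference of 3 or 5 points is not by itself evidence of a meaningful effect.

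The cost is a few sentences. Enrolment and conduct do not change. The downside is a less favourable stated figure, which fits the preliminary aim given in the Background.
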